Reference diagram	8
1. INTRODUCTION	11
1.1. BACKGROUND	11
1.2. RATIONALE FOR CURRENT STUDY	12
2. STUDY OBJECTIVES	13
3. STUDY DESIGN	13
3.1. STUDY OUTCOME MEASURES	14
4. RESEARCH PLAN	14
4.1. METHODS	14
4.2. ELIGIBILITY	14
4.3.	14
4.4. RECRUITMENT	16
4.5. WITHDRAWAL CRITERIA	17
5. ADVERSE EVENTS	17
5.1. DEFINITIONS	17
5.2. REPORTING PROCEDURES	18
6. ASSESSMENT AND FOLLOW-UP	18
7. STATISTICS AND DATA ANALYSIS	19
8. REGULATORY ISSUES	21
8.1. ETHICS APPROVAL	21
8.2. CONSENT	21
8.3. CONFIDENTIALITY AND DATA PROTECTION	21
8.4. INDEMNITY	22
8.5. SPONSOR	22
8.6. FUNDING	22
8.7. AUDITS	22
9. STUDY MANAGEMENT	22
10. PUBLICATION POLICY	22
11. REFERENCES	22
12. SUMMARY OF CHANGES	23
13. Appendix 1. REPRODUCIBILITY AND STATISTICAL DESIGN ANNEX	25

GLOSSARY OF ABBREVIATIONS

BAU	Binding Antibody Units
CPI	Confidential patient information
DABA	Double binding antigen ELISA
HES	Hospital Episode Statistics
JCVI	Joint Committee of Vaccination and Immunisation
LFIAs	Lateral flow immunoassays
NCARDRS	National Congenital Anomaly and Rare Disease Registration Service
NCRAS	National Cancer Registration and Analysis Service
NDRS	National Disease Registration Service
NHSBT	NHS Blood and Transplant
NIMS	National Immunisation Management Service
ONS	Office of National Statistics
PHE	Public Health England
REACT-2	REal-time Assessment of Community Transmission-2
RT-qPCR	Real-Time Quantitative Reverse Transcription Polymerase Chain Reaction
SACT	Systemic anti-cancer therapy
SARS-CoV-2	Severe acute respiratory syndrome coronavirus 2
SAP	Statistical analysis plan

KEYWORDS

Antibodies; Immunosuppressed; Lateral flow immunoassays; COVID-19 / SARS-CoV-2

STUDY SUMMARY

TITLE Mass evaluation of lateral flow immunoassays for the detection of SARS-CoV-2 antibody responses in immunosuppressed people (The MELODY Study)

DESIGN Observational epidemiological study

AIMS To determine:

1. The proportion of immunosuppressed people who have detectable SARS-CoV-2 antibodies following a primary vaccine course (at least 3 doses), and the demographic, disease, and treatment characteristics that influence antibody status.
2. If the detection of antibodies inversely correlates with subsequent risk of severe acute respiratory syndrome coronavirus-2 infection and/or severity of disease in immunosuppressed people.

OUTCOME MEASURES

1. The proportion of people with and without antibodies to SARS-CoV-2 at least 21 days post three vaccine doses will be presented.
2. The proportion of people with and without antibodies to SARS-CoV-2 after a 4th vaccine dose will be presented.
3. The incidence of participants having at least one RT-qPCR proven infection in the 6-month follow-up will be presented for those with and without antibodies to SARS-CoV-2 after 3rd or 4th vaccine.
4. The incidence of participants hospitalised due to COVID-19 and deaths due to COVID-19 by 6 months will be presented for those with and without antibodies to SARS-CoV-2 following 3rd or 4th vaccine, and compared as described above if there are sufficient events.
5. Rates of those with and without antibodies to SARS-CoV-2 after 3rd or 4th vaccine will be presented for different clinical characteristics and sociodemographic factors.

POPULATION Immunosuppressed people, with either:

1. A solid organ transplant
2. A rare autoimmune disease
3. A haematological malignancy

ELIGIBILITY Immunosuppressed adults (≥ 18 years old) or young persons (aged 12 to 17 years) who have received at least 3 doses of a COVID-19 vaccine.

[figure not shown]
DURATION 6 months (from the point of registration)

[figure not shown]
REFERENCE DIAGRAM

A. PARTICIPANT FLOW

B. PROCESS FLOW DIAGRAM

1. INTRODUCTION

1.1. BACKGROUND

Immunocompromised individuals make up 500,000 of the UK population and comprise diverse population groups including those with autoimmune disease, solid organ transplants, and cancer. These individuals, especially those receiving concomitant immunosuppression, have a poor prognosis to infection with SARS-CoV-2. Whilst vaccination has conferred protection against severe infections for most individuals, the immunogenicity of SARS-CoV-2 vaccines have been shown to be suboptimal in immunocompromised individuals¹⁻⁴. Although immunogenicity does not necessarily correlate with clinical efficacy, the following data supports the continued risk of COVID-19 to immunocompromised individuals: 256 COVID-19-related deaths were reported by The Office of National Statistics in doubly vaccinated individuals from January to July 2021, 13.1% of whom were immunocompromised⁵; 40% of 152 doubly vaccinated hospitalised COVID-19 patients were immunocompromised as a result of chronic corticosteroid use, solid organ transplantation or anti-cancer therapy⁶; early data from NHS Blood and Transplant (NHSBT) suggests the mortality rates from SARS-CoV-2 infected vaccinated transplant patients is as high as 8%. With these emerging data, the Joint Committee of Vaccination and Immunisation (JCVI) approved 3rd vaccine doses for immunosuppressed people, in September 2021. Existing data on serological responses to 3rd and 4th dose vaccines in immunocompromised individuals is limited, but reports suggest that up to 25% of immunosuppressed individuals will remain unprotected even after 3 doses of vaccine^{7,8}.

Serological responses to 2 vaccine doses are known to be influenced by clinical factors, such as disease type, type of immunosuppression, timing of immunosuppression in relation to vaccine and type of vaccine^{1,9}. The reported real-world clinical efficacy of SARS-CoV-2 vaccines in immunocompromised individuals in the UK is likely biased by patients' behaviour, with many continuing to self-impose shielding because of anxiety over lack of vaccine efficacy. Therefore, there is little data on true infection risk in this patient population, clinical factors contributing to lack of immunogenicity and clinical efficacy. Such information could help provide stratified advice to specific patient groups, rather than classify all immunosuppressed patients at risk. This information could also help estimate and/or identify the number of patients who may benefit from additional or alternative methods of prophylaxis, such as monoclonal antibody therapy^{10,11}.

The REal-time Assessment of Community Transmission-2 (REACT-2) study (IRAS ID 210407), used lateral flow immunoassays (LFAs) to track SARS-CoV-2 seroprevalence in the UK, coinciding with the vaccine roll out¹². Evaluating the prevalence of SARS-CoV-2 antibodies, coupled with sociodemographic information, provided informative epidemiological data. The LFAs used within the REACT-2 study

have been validated in a cohort of kidney transplant patients, with a test performance adequate to be used for population screening¹³. Using similar methodology to the REACT-2 study, we propose to investigate the proportion of immunosuppressed people with detectable SARS-CoV-2 antibodies following three and four vaccine doses, and correlate antibody status with subsequent infection risk and severity.

With the emergence of the Omicron variant, the UK government announced an expedited approach to the COVID-19 vaccination programme on 29th November 2021¹. This involved people who are severely immunosuppressed being eligible for a 4th vaccine dose 3 months after their 3rd primary dose. Early data from France, suggest that up to 42% of transplant patients will develop de novo antibody responses following a 4th dose, if they have previously been non-responsive^{2,3}. Antibody concentrations remain generally low in this population, however, and are unlikely to be associated with significant protection.

1.2. RATIONALE FOR CURRENT STUDY

Effective protection and management strategies of SARS-CoV-2 infection in immunocompromised adults have wide-reaching implications. For example, evidence has shown; a) they are more likely to have severe disease, which is associated with morbidity and mortality¹⁴⁻¹⁷; b) they are more likely to have prolonged infection, and viral shedding¹⁸; c) they are a risk for promoting viral evolution and escape mutations¹⁹.

Immunocompromised young persons (aged 12-17 years old) are also considered to be at heightened risk from SARS-CoV-2 infection. Recent studies have suggested that this group mounts stronger responses following SARS-CoV-2 vaccination than are observed in vaccinated immunosuppressed adults, but numbers of participants were small, and the Joint Committee on Vaccination and Immunisation (JCVI) has recommended that the immunocompromised young also should receive a booster vaccine following three primary vaccines⁴⁻⁶. Clarification of how this group respond to SARS-CoV-2 vaccination will inform future immunisation strategies.

The aim of this proposal is to assess at a population level; 1) the proportion of immunosuppressed people who have detectable SARS-CoV-2 antibodies following at least 3 vaccine doses, and the sociodemographic, disease, and treatment characteristics that influence antibody status; 2) if the detection of antibodies inversely correlates with subsequent risk of SARS-CoV2 infection and/or severity of disease in immunosuppressed individuals.

We aim to target patient groups least likely to mount an immune response to vaccination^{1,2,9}: a) solid organ transplant recipients; b) patients with a rare autoimmune disease; c) patients with haematological malignancies, specifically lymphoid malignancies. We will use comprehensive registries to identify and recruit patients

from these groups, and utilise the existing linkages these registries already have to obtain COVID-19 outcome information.

We hypothesise that a sizeable proportion of immunosuppressed people will have no detectable SARS-CoV-2 antibodies following either their third or fourth vaccine dose, and that this cohort is particularly susceptible to SARS-CoV-2 infection and death.

2. STUDY OBJECTIVES

AIM:

The aim of this proposal is to evaluate the detection of SARS-CoV-2 antibodies at a population level in immunosuppressed individuals, by determining:

1. The proportion of immunosuppressed people who have detectable SARS-CoV-2 antibodies following a primary vaccine course (at least 3 doses), and the demographic, disease, and treatment characteristics that influence antibody status.
2. If the detection of antibodies inversely correlates with subsequent risk of SARS-CoV-2 infection and/or severity of disease in immunosuppressed individuals.

OBJECTIVES:

1. To estimate the proportion of immunosuppressed people with detectable SARS-CoV-2 antibodies by LFIA testing following a primary vaccine course (3 doses).
2. To estimate the proportion of immunosuppressed people with detectable SARS-CoV-2 antibodies by LFIA testing following a 4th vaccine dose.
3. To correlate antibody status with risk of subsequent RT-qPCR proven infection and disease severity in immunosuppressed people.
4. To describe clinical characteristics, e.g. immunosuppression burden and sociodemographic factors, associated with lack of detectable SARS-CoV-2 antibodies.

3. STUDY DESIGN

This is an observational epidemiology study, combining self-reported near patient testing results, questionnaire data and routinely collected electronic health records.

Duration of study: 12 months

Number of participants: 36,000 immunosuppressed adults, and 750 immunosuppressed young adults (12-17 years old).

3.1. STUDY OUTCOME MEASURES

1. The proportion of participants with and without antibodies to SARS-CoV-2 at least 21 days post 3rd vaccine will be presented.
2. The proportion of people with and without antibodies to SARS-CoV-2 after a 4th vaccine dose will be presented.
3. The incidence of participants having at least one RT-qPCR proven infection in the 6-month follow-up will be presented for those with and without antibodies to SARS-CoV-2 after 3rd or 4th vaccine.
4. The incidence of participants hospitalised due to COVID-19 and deaths due to COVID-19 by 6 months will be presented for those with and without antibodies to SARS-CoV-2 following 3rd or 4th vaccine, and compared as described above if there are sufficient events.
5. Rates of those with and without antibodies to SARS-CoV-2 after 3rd or 4th vaccine will be presented for different clinical characteristics and sociodemographic factors.

4. RESEARCH PLAN

4.1. METHODS

We propose to undertake a survey of seroprevalence using self-administered lateral flow assays in 36,000 immunosuppressed adult participants and 750 young people, who are at least 21 days after completion of their primary COVID-19 vaccination course (3 vaccines of which may include a mix of vaccine types). People who have received a 4th booster dose, will also be included. Infection data will be recorded over a 6-month period (from the date of registration).

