6. ASSESSMENT AND FOLLOW-UP

Direct participant involvement will finish after the results of the LFIA test are uploaded. Follow up thereafter will be via the respective registries for 6 months. The study will end at the time the last participant reaches 6 months from the point of their registration on the study web portal.

Participants will have access to an information booklet which describes the meaning of the test results. Participant's GPs will not be informed of recruitment.

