7. STATISTICS AND DATA ANALYSIS

Data collection will be undertaken in collaboration with implementation partner Ipsos MORI. The data from the participants is self-entered into an online questionnaire hosted on a secure web portal developed and managed by Ipsos MORI.

Ipsos MORI will be responsible for setting up and managing the study web portal, receiving the questionnaire data, setting up and entering the questionnaire data into the study database and linking in the uploaded results of lateral flow assay. Once data is complete, a copy of the study database for each patient population will be sent securely from Ipsos MORI to NHSBT and NDRS where it will be linked to routinely collected healthcare data on COVID-19 infection, and severe outcome over the subsequent 6 months and analysed.

Analysis for the a) solid organ transplant groups and b) rare autoimmune disease and cancer groups will be conducted using a common protocol and statistical analysis plan, but separately by NHSBT and NDRS respectively, due to the complexities of data sharing between the two registries and existing restrictions on the data sharing they have with NIMS and NHS Digital. The high-level analysis plan is as follows:

1. The proportion of patients (and 95% CI) with and without antibodies to SARS-CoV-2 at least 21 days post 3rd vaccine and prior to 4th vaccine dose will be presented.
2. The proportion of patients (and 95% CI) with and without antibodies to SARS-CoV-2 following a 4th vaccine dose will be presented
3. The cumulative incidence (and 95% CI) of participants having at least one RT-qPCR proven infection in the 6-month follow-up will be presented for those with and without antibodies to SARS-CoV-2 at the time the study LFIA was undertaken. Risk-adjusted cumulative incidence rates will be compared using a Fine and Gray model. These methods allow for participants who may die during the follow-up period.
4. The cumulative incidence (and 95% CI) of participants hospitalised due to COVID-19 and deaths due to COVID-19 by 6 months will be presented for those with and without antibodies to SARS-CoV-2 at the time the study LFIA was undertaken and compared as described above if there are sufficient events.
5. Rates of those with and without antibodies to SARS-CoV-2 after 3rd or 4th vaccine (and 95% CI) will be presented for different clinical characteristics and

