sociodemographic factors. Logistic regression models will be used to identify which of these factors are independently associated with developing antibodies following completion of the primary vaccine course.

6. The proportion of re-sampled transplant recipients (and 95% CI) with and without antibodies to SARS-CoV-2 following 4th dose who did not have antibodies after 3rd dose.

All outcomes will be adjusted for other known risk factors, and receipt of a subsequent 4th vaccine dose, as and where appropriate. Multiple imputation based on full conditional specification will be used to impute values of potential risk adjustment factors. The set of variables that will feature in the multiple imputation models will be described in the SAP. Sensitivity analyses will be conducted with cases with missing primary outcome data excluded.

A descriptive analysis aligned with above will additionally be performed for the young adult population.

Sample size

Each participant population will recruit 12,000 participants, and of these, we expect 85% to return their LFIA result (n=10,200). Following a third vaccine, we estimate approximately a third of participants in each group will have no SARS-CoV-2 antibodies, so this sample size will give a 95% confidence interval for the proportion of participants with no antibodies of $\pm 0.91\%$ for each participant group ^{7,8}. Even if the proportion of participants with no antibodies is 50%, the confidence interval would be $\pm 0.97\%$, so the large study size gives very good precision.

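### The plan gives two conflicting clocks for infection follow-up, registration and the LFIA, and sets no time origin for the comparison by antibody status

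*Combined protocol and SAP*

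**What the plan says.** Three places count from registration. Section 4.1 has "Infection data will be recorded over a 6-month period (from the date of registration". The Study Summary gives the duration as "6 months (from the point of registration". Section 6 has "The study will end at the time the last participant reaches 6 months from the point of their registration on the study web portal".

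Other wording points to a start after the test. In section 6, directly after the statement that participants' involvement ends once the LFIA result is uploaded, comes "Follow up thereafter will be via the respective registries for 6 months". Section 7 describes linkage to "COVID-19 infection, and severe outcome over the subsequent 6 months" once uploaded LFIA results are in the database. Objective 3 in section 2 concerns *subsequent* infection.

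The order of steps is fixed in section 4.3: registration, then the questionnaire, then dispatch of the kit. No maximum interval is given. Section 7, items 3 and 4, compares "those with and without antibodies to SARS-CoV-2 at the time the study LFIA was undertaken". Item 3 names a Fine and Gray model but no time origin.

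The transplant cohort is analysed by NHSBT and the other two by NDRS, "conducted using a common protocol and statistical analysis plan". Section 7 calls its own list high-level and refers to a SAP outside this document, for example in "The set of variables that will feature in the multiple imputation models will be described in the SAP".

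**The concern.** A cohort comparison by baseline exposure needs its clock to start when the exposure is measured. Here one stated clock starts earlier. If it is used for the analysis, three things follow.

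- Infections between registration and LFIA count as outcomes although they precede the antibody measurement. Objective 3 is about infections after it.
- The device detects antibody to the spike protein (Appendix 1), so an infection in the gap could itself turn the test positive. A participant who would have been antibody-negative then enters the antibody-positive group carrying an event, and antibodies look less protective than they are. A larger sample does not remove this bias.
- A participant must be alive to do the test and be classified, so the time from registration to test is immortal for the death outcome in item 4.

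The infection history in section 4.3 is taken at the questionnaire, before the kit is sent, so it does not cover the gap. Because two organisations analyse separately, an unstated origin could also be implemented differently in each.

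**Working it through.** **Inputs from the document.** Infection over 180 days is 7.6% with antibodies and 9.6% without. The ratio is 2:1, the test is two-sided at 5%, power is 90%, and 9,273 participants are required per population against 10,200 expected LFIA results (section 7 and Appendix 1).

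**The plan's own figures.** Event rate: 0.79% × 180/28 = 5.08%, and × 1.5 = 7.62%, hence 92.4% infection-free. Sample size by two proportions, with pooled rate (0.096 + 2 × 0.076)/3 = 0.0827:

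n(negative) = [1.96 √(0.0827 × 0.9173 × 1.5) + 1.2816 √(0.096 × 0.904 + 0.076 × 0.924/2)]² / 0.02² = 3,072, total 9,216.

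This is within 1% of 9,273, so the sample size is not in question. By the same method, power is 90.2% at 9,273 and 92.6% at 10,200.

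**Assumed, because the document does not give them.** The gap g from registration to LFIA, the lag from infection to detectable antibody, and the share s of antibody-negative people infected earlier than the lag who test positive as a result.

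**Infections before the test.** Expected infections at 9,273: 3,091 × 0.096 + 6,182 × 0.076 = 296.7 + 469.8 = 766.6. At 10,200: 326.4 + 516.8 = 843.2. With infections spread evenly, the fraction before the test is g/180. For g = 14 this is 7.8%: about 60 of 767, or 66 of 843.

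**Effect on the contrast.** Number moved: m = negative events × max(0, g − lag)/180 × s. The negative rate becomes (events − m)/(n − m) and the positive rate (events + m)/(n + m).

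Example at 9,273 with g = 14, lag 10, s = 0.25: m = 296.7 × 4/180 × 0.25 = 1.65. The rates are 295.1/3,089.4 = 9.55% and 471.5/6,183.6 = 7.62%, a difference of 1.93 points.

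| Gap, lag, share converting | Difference (points) | Power at 9,273 | Power at 10,200 |
|---|---|---|---|
| 14 days, lag ≥ 14 days, any share | 2.00 | 90.2% | 92.6% |
| 14 days, 10 days, 25% | 1.93 | 88.0% | 90.8% |
| 14 days, 0 days, 10% | 1.90 | 87.1% | 89.9% |
| 14 days, 0 days, 25% | 1.74 | 81.3% | 84.7% |
| 28 days, 10 days, 25% | 1.67 | 78.0% | 81.6% |

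Zero lag is the extreme value of the lag, so the fourth row is an upper illustration for a 14-day gap at that share. A longer gap or a larger share would shrink the difference further. Section 1.2 describes these groups as the least likely to respond to vaccination, which argues for a low share.

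**Power under the two remedies, 14-day gap.**
- A full 180 days from the LFIA, with everyone infected in the gap removed: 90.0% at 9,273 and 92.4% at 10,200.
- Delayed entry at the LFIA with the end date unchanged, so 166 days at constant hazard: rates 1 − 0.904^(166/180) = 8.89% and 1 − 0.924^(166/180) = 7.03%, giving 87.9% and 90.7% (87.7% and 90.5% if people infected in the gap are removed).

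**The case against.** The strongest reply is that the intended clock is visible. In section 6 the word *thereafter* refers back to upload of the LFIA result, and objective 3 and section 7 speak of subsequent events. The registration wording gives a study duration, a study end and a recording window. None of these need be the analysis origin, and items 3 and 4 of section 7 do not mention registration. Time origin is also ordinary SAP content.

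Much of this stands. A reader might infer that the plan, as written, counts infections before the test as outcomes. The document does not support that: following section 6 would exclude them. Nor can it be said that no rule exists, only that none appears here.

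It does not remove the conflict. Section 6 promises six months after the test but ends the study six months after the last registration, and both cannot hold in full for the last registrants. A SAP rule starting at the LFIA would leave section 4.1 needing reconciliation.

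A reader might also infer that test dates are not collected, because section 4.3 mentions only the return of results. That is an inference from silence: section 4.3 does not list the portal fields, and item 1 of section 7 presupposes knowledge of when the test was done.

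**Conclusion.** The point holds as an unresolved time origin with two conflicting clocks, and it should be settled before the outcome analysis. It is not a demonstrated error in the analysis.

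If the registration clock is used, any bias from seroconversion in the gap runs towards no protection. Its size is unknown because gap, lag and share converting are all assumed. For a 14-day gap the planned 2-point difference ranges from unchanged to 1.74 points over the cases shown. The effect is small if kits are used quickly and could be material if the gap runs to several weeks, but the document supports no particular gap. A reader might take the lower power figures as expected performance; they are illustrations only. Even where the difference is unchanged, the outcome would include events that precede the exposure measurement.

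**What to change.** - Reconcile the Study Summary duration, section 4.1, section 6 and section 7.
- In the common protocol and SAP, set time zero for outcomes 3 and 4 at the date of the LFIA that defines the group. State whether this is the initial LFIA, given that item 6 of section 7 analyses the transplant retest separately.
- Count only infections, hospitalisations and deaths after time zero. Treat infections between registration and LFIA as baseline infection history, and report their number and the distribution of the interval.
- Confirm that the LFIA date is captured. For results already returned without one (section 4.3 reports 2,500 transplant results by 14 February 2022), use the result-upload date.
- Choose the end of follow-up: either six months from the LFIA, or delayed entry at the LFIA with the present end date.

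Cost: wording, and possibly one portal field; recruitment is unchanged. Six months from the LFIA extends passive linkage by the kit turnaround. It changes the durations in the Study Summary and section 6, and possibly the 12 months in section 3, with power about 90% at 9,273 and 92% at 10,200. Delayed entry leaves the end date alone and, for a 14-day gap, gives about 88% and 91%. The upload-date fallback starts the clock slightly late and loses any infection between test and upload.
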